5.9.3. Clinical Laboratory Collection and Analysis

Laboratory samples will be collected under the following conditions:

- Blood samples will be drawn prior to the study drug infusion on infusion visits, and in the morning (whenever feasible) on noninfusion visits;
- Subjects ≥ 18 will fast for at least 9 hours prior to collection of blood samples;
- Subjects will refrain from ingestion of alcohol for 24 hours prior to collection of blood samples for lipid and liver panels.

Refer to the SOM and Laboratory Manual for further details regarding the collection, processing, and storage of clinical laboratory samples.

A central laboratory will be responsible for analysis of all laboratory tests, with the exception of prothrombin time (international normalized ratio), activated partial thromboplastin time, urinalysis, and urine pregnancy.

Any identified laboratory abnormalities will be specified as CS or NCS by the Investigator or designee. In the event of unexplained clinically significant abnormal laboratory test results, the tests will be repeated as soon as possible (preferably within 24 hours of receiving the result) and followed up until they have returned to within the normal range and/or an adequate explanation has been identified. Clinically significant changes from a subject's baseline value or previous values will be recorded as AEs.

5.9.4. Clinical Laboratory Collection for Dose Changes

Subjects who undergo a dose modification, as described in [Section 6.1](#), or changes in lipid-lowering therapies, as described in [Section 4.5](#), will have the following additional laboratory monitoring schedule of selected analytes:

- Prior to the first infusion of new dose/schedule or change in lipid-lowering medication: serum lipid panel, liver panel, hematology, serum chemistry, ferritin, hs-CRP;
 - For dose modifications only: at the first infusion of new dose/schedule, a predose blood sample will be collected for ADA and serial blood samples will be collected for a determination of sebelipase alfa serum concentrations according to the sampling schedule shown in [Table 2](#) (pediatric subjects) or [Table 3](#) (adult subjects).
- 4 weeks after starting new dose/schedule or change in lipid-lowering medication: serum lipid panel, liver panel;
- 8 weeks after starting new dose/schedule or change in lipid-lowering medication: serum lipid panel, liver panel;
- 12 weeks after starting new dose/schedule or change in lipid-lowering medication: serum lipid panel, liver panel, hematology, serum chemistry.

In the event that any of the above additional laboratory monitoring time points coincides with the standard laboratory assessment, the standard laboratory assessment will supersede the additional laboratory monitoring (see [Appendix B](#)).

If a subject's blood volume threshold for weight or clinical status limit collection of samples on the scheduled visit date, the Sponsor or medical monitor should be consulted for guidance with regard to a modified schedule for that visit.

Table 1 Clinical Laboratory Tests

| Laboratory Panel | Tests |
|---|---|
| Hematology | White blood cell count; red blood cell count; hemoglobin; hematocrit; mean corpuscular volume, hemoglobin, and hemoglobin concentration (MCV, MCH, MCHC); platelet count; neutrophil; lymphocytes; monocytes; eosinophils; basophils; peripheral smear for examination of cell morphology |
| Liver Function Tests | ALT, AST, alkaline phosphatase, GGT, albumin, bilirubin (direct, indirect, total) |
| Serum Lipids | LDL-C, total cholesterol non-HDL-C, triglyceride, HDL-C |
| Other Chemistries | Serum electrolytes (sodium, potassium, chloride, calcium, magnesium, phosphorus), glucose, creatinine, bicarbonate, total protein, blood urea nitrogen, hs-CRP |
| | HbA1c |
| Macrophage Activation Markers | serum chitotriosidase, serum ferritin, hs-CRP, CK-18 |
| Urinalysis ¹ | pH, clarity, color, specific gravity, glucose, ketones, blood, protein, nitrite, and leukocytes (microscopic examination will only be done if urinalysis is positive for blood, nitrite, or leukocytes, or if protein is >1+) |
| Viral Hepatitis Screen | HBsAg and HCV serology |
| Alcohol Use | CDT |
| Coagulation Parameters ¹ | PT (INR), aPTT |
| Pregnancy ² | Serum hCG at Screening and urine hCG ¹ at all other visits |
| Anti-drug Antibody | Anti-sebelipase alfa antibody |
| Exploratory Biomarkers | See Section 5.9.5 . |
| LAL Enzyme Activity | Dried blood spot. See Section 5.9.6 . |
| DNA Sample | See Section 5.9.7 |
| PK Samples | See Section 5.9.4 |
| Malnutrition Markers and Fat Soluble Vitamins | See Laboratory Manual for details |

¹ Test performed by a local laboratory.

² Performed for female subjects of childbearing potential only. In the event of a positive pregnancy test result, refer to [Section 7.2.3](#) for information on pregnancy reporting and follow-up.

5.9.5. Exploratory Biomarkers

Blood samples (for serum isolation) will be obtained at the time points specified in [Appendix B](#), where local regulations and blood volume limitations permit, for exploratory analyses to identify and evaluate disease-related biomarkers.

Biomarker assays will be performed by a central laboratory or, as appropriate, by academic research laboratories with expertise in the analysis of specific biomarkers. The intent is to investigate baseline disease and dynamic markers that will enable the Sponsor to better understand the pathogenesis of LAL Deficiency and related comorbidities and response to sebelipase alfa therapy. Given the rarity of LAL Deficiency and the paucity of information on disease characteristics, the definitive list of analytes remains to be determined.

Collection of samples for exploratory biomarker analysis will be subject to discretionary approval from each center's IRB/IEC and the specific written consent of the subject and/or the subject's parent or legal guardian. This section of the protocol only applies if approval for collection of these additional samples has been granted by the IRB/IEC and consent is provided by the subject (or the subject's parent or legal guardian).

Samples will be stored by the Sponsor or designee in a secure and controlled environment until analysis, and will be destroyed by the Sponsor or designee after all worldwide obligations have been met, or sooner if required by local regulations.

Refer to the SOM or Laboratory Manual for further details regarding the collection, processing, and storage of these samples.

5.9.6. LAL Enzyme Activity in Dried Blood Spots

A blood sample will be spotted on filter paper at the site for each subject and then shipped to the central laboratory for measurement of DBS LAL enzyme activity. A sample will be collected from all subjects, irrespective of whether historical LAL activity data are available. For subjects who have undergone liver transplantation the DBS will be performed, but it will not be used to determine study eligibility. Samples will be collected at the time points specified in [Appendix B](#).

All samples will be assayed by a central laboratory to ensure consistency of LAL activity measurements across all subjects in the study. Refer to the SOM and Laboratory Manual for further details regarding the collection, processing, and storage of this sample.

5.9.7. DNA Sample

The Sponsor intends to analyze pharmacogenetics in the sebelipase alfa program in order to explore how genetic variations may affect clinical parameters associated with sebelipase alfa use and LAL biology. DNA sequences, including both the protein coding sequence and sequences that regulate gene transcription, messenger ribonucleic acid stability and the efficiency of protein translation that may be investigated include:

1. LAL (LIPA);

Genes coding for other proteins involved in lipid biology that may contribute to and/or modify the disease phenotype of LAL Deficiency (e.g. ABCA1);

2. Genes that may modify susceptibility to AEs related to sebelipase alfa.

Where local regulations permit and subject to discretionary approval from each center's IRB/IEC, a blood sample for DNA extraction will be collected from each subject at Screening, or as soon as practically possible thereafter, for subjects who do not require sample collection to establish study eligibility. The DNA will be used as part of a later pooled analysis, which will include a determination of the spectrum of LAL mutations in subjects with LAL Deficiency and the relationship between gene mutation, safety, efficacy, and susceptibility to development of ADAs. The Sponsor will only analyze DNA sequences within genes relevant to the mode of action and response to sebelipase alfa, including variants important in understanding AEs, and candidate genes with a potential role in the etiology, pathogenesis, and progression of LAL Deficiency. No additional testing will be performed on the samples collected in the study.

DNA samples will be stored by the Sponsor, or designee, in a secure, monitored, and controlled environment until analysis, and will be destroyed by the Sponsor after all worldwide obligations have been met, or sooner if required by local regulations.

Refer to the SOM and Laboratory Manual for further details regarding the collection, processing, and storage of these samples.

5.9.8. Pharmacokinetic Assessments

Blood samples for determination of sebelipase alfa serum concentrations will be collected from subjects < 18 years of age, from subjects with severely impaired liver functioning (e.g. based on imaging, biopsy or Child-Pugh Class C status at Screening), and for subjects who have previously undergone liver or hematopoietic stem-cell transplantation. Sampling will be completed as blood volume permits (see [Section 5.9](#)) at Baseline, Week 24 and Week 48, and on the day of a dose modification, as applicable. If a subject's blood volume threshold for weight or clinical status limit collection of samples on the scheduled visit date, the Sponsor or medical monitor should be consulted for guidance with regard to a modified schedule.

A sparse sampling scheme will be employed for pediatric subjects (< 18 years of age at informed consent) to reduce the risk of iatrogenic anemia. As shown in [Table 2](#), up to 4 blood samples will be collected at each study visit requiring a PK assessment. These samples will be collected within broad time windows, rather than at discrete time points, to allow more flexibility in the management of PK sampling for these subjects and to provide opportunities for measurement of drug concentrations across a broader time period with limited sampling.

A more extensive sampling scheme will be employed for adult subjects (≥ 18 years of age at informed consent) with severe liver disease, and those who have received a hematopoietic stem cell or liver transplant, in order to assess the PK profile in this population of adult subjects previously not evaluated in other clinical studies of sebelipase alfa. As shown in [Table 3](#), up to 12 blood samples will be collected from these adult subjects at each study visit requiring a PK assessment. A majority of these samples will be collected at discrete time points.

PK samples will not be taken from the extremity used for the study drug infusion. PK sampling at time points that coincide with a vital sign measurement will be obtained before cuff inflation for the blood pressure measurement, and PK samples at other time points will be obtained at least 5 minutes after cuff deflation. The exact start time and stop time of each infusion and the exact time of collection of each sample will be recorded in the eCRF.

Refer to the SOM and Laboratory Manual for further details regarding the collection, processing, and storage of these samples.

Table 2 PK Sampling in Pediatric Subjects (Age < 18 Years at Informed Consent)

| | Week 0 | Week 24 | Week 48 | Dose Modification |
|--|--------|---------|---------|-------------------|
| During Infusion | | | | |
| 0 hour to end of infusion ¹ | X | X | X | X |
| After Completion of Infusion | | | | |
| 0 to 30 minutes | X | X | X | X |
| 30 minutes to 1 hour | X | X | X | X |
| 1 to 2 hours | X | X | X | X |

¹ A sample will be obtained any time after the start of the infusion up until the end of the infusion (i.e., after the infusion bag has been emptied, but prior to the sodium chloride flush).

Table 3 PK Sampling in Select Adult Subjects (Age ≥ 18 Years at Informed Consent)

| | Week 0 | Week 24 | Week 48 | Dose Modification |
|--|--------|---------|---------|-------------------|
| Pre-infusion | | | | |
| Within 30 minutes before start of infusion | X | X | | X |
| During Infusion¹ | | | | |
| 15 minutes (±5 minutes) | X | | | X |
| 30 minutes (±5 minutes) | X | X | | X |
| 1 hour (±5 minutes) | X | | | X |
| End of infusion ² (±5 minutes) | X | X | X | X |
| After Completion of Infusion | | | | |
| 5 minutes (±2 minutes) | X | X | | X |
| 10 minutes (±2 minutes) | X | X | | X |
| 15 minutes (±2 minutes) | X | X | | X |
| 30 minutes (±5 minutes) | X | X | | X |
| 45 minutes (±5 minutes) | X | X | | X |
| 1 hour (±5 minutes) | X | X | | X |
| 2 hours (±5 minutes) | X | X | | X |
| 0 to 1 hour | | | X | |
| 1 to 2 hours | | | X | |

¹ Sampling times are relative to the start of the infusion.

² After the infusion bag has been emptied, but prior to the sodium chloride flush.

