1.4.1. Completed Study LAL-CL01

LAL-CL01, the first clinical study with sebelipase alfa, evaluated the safety, tolerability, and pharmacokinetics (PK) of sebelipase alfa following a 4-week regimen of once-weekly (qw) IV infusions of sebelipase alfa at doses of $0.35 \text{ mg}\cdot\text{kg}^{-1}$, $1 \text{ mg}\cdot\text{kg}^{-1}$, and $3 \text{ mg}\cdot\text{kg}^{-1}$ in adult subjects with liver dysfunction due to LAL Deficiency. A total of 9 subjects were enrolled into 3 sequential cohorts of 3 subjects each.

All 3 doses of sebelipase alfa were well tolerated by the subjects in this study. There were no deaths or treatment-emergent serious adverse events (SAEs), and no subject experienced an infusion-associated reaction (IAR) or discontinued treatment due to a treatment-emergent adverse event (TEAE). Most (86.4%) of the 44 reported TEAEs were considered unrelated to sebelipase alfa, and all but one were assessed by the Investigator as Grade 1 (86.4%) or Grade 2 (11.4%) in severity. One subject in the $3 \text{ mg}\cdot\text{kg}^{-1}$ dose cohort had a Grade 4 TEAE of hypercholesterolemia. Although the subject was asymptomatic, this laboratory abnormality met the definition of a Grade 4 event according to Common Terminology Criteria for Adverse Events (CTCAE), which was used to assess severity in this study.

All 3 doses of sebelipase alfa were biologically active, as evidenced by decreases in alanine aminotransferase (ALT) and aspartate aminotransferase (AST) and increases in serum lipids (total cholesterol, triglycerides, and LDL-C), which were observed within 2 and 4 weeks, respectively, and were reversible following discontinuation of sebelipase alfa therapy. Effects on serum lipids appeared more pronounced in the $3 \text{ mg}\cdot\text{kg}^{-1}$ dose cohort, whereas effects on ALT and AST appeared to be independent of dose.

PK data in adult subjects with LAL Deficiency indicate that sebelipase alfa has a short plasma half-life, ranging from 0.07 to 2.04 hours at the lowest dose of $0.35 \text{ mg}\cdot\text{kg}^{-1}$ and from 0.09 to 0.21 hours at higher doses of 1 or $3 \text{ mg}\cdot\text{kg}^{-1}$. Sebelipase alfa area under the concentration-time curve (AUC) and maximum observed concentration (C_{max}) increased proportional to dose from 0.35 to $1 \text{ mg}\cdot\text{kg}^{-1}$ and more than proportional to dose from 1 to $3 \text{ mg}\cdot\text{kg}^{-1}$.

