8.9.3. PK Analysis in Pediatric Subjects (Age <18 Years at Informed Consent)

Serum concentrations of sebelipase alfa will be summarized in a descriptive manner. Scatter plots may be used and where appropriate concentrations may be summarised by collection interval, in addition to dose and dosing regimen.

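### The pediatric PK sampling windows fit poorly with the only half-life the protocol gives at 1 or 3 mg/kg, and a summary by collection interval would mix large differences due to timing alone

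*Protocol*

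**What the plan says.** Pediatric PK is an exploratory objective (Protocol 2.3). Section 5.9.8 sets a sparse scheme for everyone under 18 at consent: "up to 4 blood samples will be collected at each study visit requiring a PK assessment". It adds: "These samples will be collected within broad time windows, rather than at discrete time points". The stated reasons are to limit iatrogenic anemia, to give sites flexibility and to cover a broader time span.

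Table 2 has the same four rows at Week 0, Week 24, Week 48 and dose modification. For the during-infusion row, "A sample will be obtained any time after the start of the infusion up until the end of the infusion". The first post-infusion row is "0 to 30 minutes"; the others are 30 minutes to 1 hour and 1 to 2 hours. Exact infusion and collection times are recorded in the eCRF.

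Adult Table 3 has discrete samples at 5, 10, 15, 30 and 45 min, 1 h and 2 h after infusion at Week 0, Week 24 and dose modification. At Week 48 it uses windows of 0–1 h and 1–2 h.

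The half-life evidence is in 1.4.1: "PK data in adult subjects with LAL Deficiency indicate that sebelipase alfa has a short plasma half-life, ranging from 0.07 to 2.04 hours" at 0.35 mg/kg, and "from 0.09 to 0.21 hours at higher doses of 1 or" 3 mg/kg. That study was small: "A total of 9 subjects were enrolled into 3 sequential cohorts of 3 subjects each".

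Section 8.9.3 makes the pediatric analysis descriptive. Scatter plots are optional, and "where appropriate concentrations may be summarised by collection interval". Section 8.9.1 sends concentrations to a population PK model reported outside this study. SAP 5.3 and 7.4 defer PK to a separate analysis plan.

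**The concern.** A half-life of 0.09–0.21 h is 5.4–12.6 minutes, and the post-infusion windows are 30, 30 and 60 minutes wide. Two things follow.

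First, the samples may fall where little drug is left. A child can comply fully with Table 2 and have nothing drawn in the first minutes, when most of the decline would take place. The adult schedule samples there three times at most PK visits. With only four draws, their placement matters more than it does for adults.

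Second, pooling concentrations by window puts values from very different points on the curve into one mean or median. The result would depend heavily on when the sample happened to be drawn.

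At stake is how well this study can describe exposure in children. Section 3.2.1.3 expects descriptive PK parameters for subjects under 18, as data permit, whereas 8.9.3 provides only for concentrations.

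**Working it through.** **Inputs.** Half-life at 1 or 3 mg/kg: 0.09–0.21 h (Protocol 1.4.1). Half-life at 0.35 mg/kg: up to 2.04 h (same place). Windows: Table 2. Infusion length: about 2 h up to Week 24, optionally about 1 h afterwards (6.1). The LLOQ and the end-of-infusion concentration are not given.

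**Unit check.** 0.09 × 60 = 5.4 min; 0.21 × 60 = 12.6 min; 2.04 × 60 = 122.4 min. The protocol states no figure for the windows themselves, so there is no plan result to reproduce.

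**Assumptions.** The adult half-life applies to children, and decline after the infusion is mono-exponential.

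**1. Share of the end-of-infusion level left at time t:** 2^(−t / half-life).

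| Time after infusion | Half-life 5.4 min | Half-life 12.6 min |
|---|---|---|
| 30 min | 2.1% | 19.2% |
| 60 min | 0.045% | 3.7% |
| 120 min | 0.00002% | 0.14% |

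The 1–2 h window opens 60/12.6 = 4.8 to 60/5.4 = 11.1 half-lives after the infusion. It closes at 9.5 to 22.2.

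**2. A compliant but late set of draws.** Samples at 25, 55 and 115 min satisfy Table 2. They would find about 4–25%, 0.09–4.9% and at most 0.18% of the end-of-infusion level.

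**3. Fold-difference across a window of width w from time alone:** 2^(w / half-life).
- Each 30-minute window: 2^(30/12.6) = 5.2 to 2^(30/5.4) = 47.
- The 1–2 h window: 2^(60/12.6) = 27 to 2^(60/5.4) = about 2,200, if the values are measurable.

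**4. The during-infusion sample:** share of plateau = 1 − 2^(−t / half-life). At 5 min into the infusion this is 24–47%; at 60 min it is 96–100%. A draw at any time in the infusion can therefore fall well short of plateau, while one near the end would not.

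**5. Time until the level reaches the LLOQ:** half-life × log2(end-of-infusion level / LLOQ). The ratio is an assumption, so a range is shown.

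| Assumed ratio | Half-life 5.4 min | Half-life 12.6 min |
|---|---|---|
| 10 | 18 min | 42 min |
| 100 | 36 min | 84 min |
| 1000 | 54 min | 126 min |

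In four of these six cases the level is below the LLOQ before the 1–2 h window opens. In one it is measurable for part of that window (to 84 min), and in one throughout. For the 30–60 min window, one case is below throughout, three are measurable for part of it and two throughout.

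**6. The 0.35 mg/kg dose.** With a half-life of 2.04 h, 84% is left at 30 min, 71% at 1 h and 51% at 2 h. Late samples would then be informative. If the last sample came at 40 min, 2^(−40/122.4) = 80% would still be left, and half-life would be poorly estimable.

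**The case against.** The strongest reply is that the calculation assumes what the study is meant to find out. The half-life comes from three adults per dose, and no pediatric value is given. Section 1.4.1 also reports exposure rising more than in proportion to dose from 1 to 3 mg/kg, which makes one mono-exponential half-life doubtful. At 0.35 mg/kg, which the protocol permits and for which Table 2 has a dose-modification column, the half-life reached 2.04 h. This stands as a reason to keep one later sample. It does not justify leaving the early minutes uncovered: the short half-life is the only evidence in the documents for the starting dose, and every subject starts at 1 mg/kg.

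The second reply concerns the analysis. The by-interval summary is permitted, not required. Exact times are recorded, and the concentrations go to a population PK model that can use those times, for which spread within windows can help. A separate PK plan, not available here, may add more. This limits the harm considerably. A model still cannot recover information from values too low to measure, and its results lie outside this study's reporting. In the protocol, 8.9.3 is the only pediatric PK analysis reported within the study.

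The third reply is that the windows were chosen deliberately, for reasons that 5.9.8 gives, and that adult sampling also runs to 2 h. That is fair. But the adult schedule adds early samples at most PK visits, and the pediatric one requires none.

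**Conclusion.** The concern holds in a limited form. At 1 or 3 mg/kg the windows are wide against the only half-life available. The 1–2 h sample is likely to be of low yield, with at most 3.7% of the end-of-infusion level left when its window opens and 0.14% when it closes. No early post-infusion sample is assured. A summary by interval would carry 5- to 47-fold differences from timing in each 30-minute window and 27- to about 2,200-fold in the last. All of this rests on adult half-lives from three subjects per dose and on mono-exponential decline.

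A reader might infer more than this, and the documents do not support it:
- That two of the four samples carry almost no information. At a half-life of 12.6 min, 19% down to 3.7% is left across 30–60 min, and without the LLOQ that sample cannot be written off.
- That pediatric clearance and half-life rest on a single usable value per visit. This ignores the during-infusion sample, which near plateau informs clearance directly, and pooling across subjects in the population model.
- That the by-interval summary is the planned analysis. It is optional.
- That late sampling should be dropped. The unknown pediatric half-life and the 0.35 mg/kg data argue against that.
- That only small children are affected. Table 2 covers everyone under 18.

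The point is a low-cost improvement to an exploratory objective. It does not touch the primary safety evaluation.

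**What to change.** 1. In Protocol 8.9.3, and in the separate PK plan if it repeats that text, plot and summarise pediatric concentrations by actual time since the start or end of infusion, not by collection interval. The times are already collected, so this costs one sentence.

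2. In Table 2, keep four samples for subjects under 18 but re-time them:
   - one near the end of the infusion;
   - one early after it, for example 0–10 min;
   - one at about 10–30 min;
   - one later sample, with its window justified against the assay LLOQ and the possibility of a longer half-life.

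Under the same assumptions, 28–58% of the end-of-infusion level is left at 10 min (2^(−10/5.4) and 2^(−10/12.6)). Time alone then moves the level 1.7- to 3.6-fold within 0–10 min and 3- to 13-fold within 10–30 min (2^(20/12.6) and 2^(20/5.4)). Actual time is therefore still needed in the summary.

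The cost is an amendment to one table and one sentence, and no extra blood. Sites would have tighter windows. These must fit around the vital signs taken every 30 minutes after infusion (5.7) and the rule in 5.9.8 that PK samples come before cuff inflation or at least 5 minutes after deflation. The example times come from the half-life arithmetic alone. A check of the sampling design against the population model should confirm them before the amendment.
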